The primary objectives of this trial will be to compare rates of self-reported, symptomatic volume GOR and objectively measured rates of volume GOR using scintigraphy, between the two study groups. This will be a superiority trial, with the hypothesis being that palliative oesophageal anti-reflux self-expanding fully covered metal stents significantly reduce volume GOR compared to conventional oesophageal self-expanding fully covered metal stents.

Secondary Objectives

Secondary objectives will be to compare outcomes, including rates of dysphagia, cough, pain, stentrelated complications, subsequent complications and patient survival at the end of the study period. A further objective will be to compare the self-reported GOR questionnaire (GerdQ) outcomes to the objectively measured oesophageal scintigraphy measurements.

METHODS

Trial Design

This study will be a prospective randomised controlled trial comparing anti-reflux oesophageal stents to conventional oesophageal stents. Randomisation to an anti-reflux stent versus a conventional stent will be done prior to stent placement and the patient will remain blinded to the type of stent placed. Although the authors will not be blinded to the stent type, as the stents are easily distinguished from each other at the time of endoscopy, the Clinical Coordinator who will be doing the follow-up will be blinded to this. This study will be performed following the CONSORT 2010 checklist of information for randomised trials ²².

Once the study is approved by the University of Cape Town's Human Research Ethics Committee, approval for the study will also be obtained from Groote Schuur Hospital. The trial will then be registered with the South African National Clinical Trials Register (SANCTR) and at clinicaltrials.gov. Both stents being compared in this trial are already approved by the South African Health Products

Regulatory Authority (SAHPRA), and as they form part of standard of care, application to SAHPRA will not be necessary.

Participants

Eligibility criteria for trial participants:

Inclusion Criteria (all criteria must be met):

- Adult patients 18 years of age or older
- Informed consent obtained from the patient after oral and written explanation of the trial
- Histologically confirmed malignancy of the distal oesophagus or OGJ
- Obstructive or irresectable malignancy due to metastases, local tumour infiltration or poor performance status

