Patients with palliative oesophageal cancer are in most instances frail and have a significantly limited life expectancy. It is thus imperative upon discharge, that further research-related follow-up should not inconvenience the patient nor have a negative effect on their quality of life. Furthermore, many of the patients treated at GSH have limited financial means to afford repeated follow-ups at the hospital. For these reasons, subsequent follow-up after discharge, will be done telephonically. Patients will be phoned at 1, 2, 4 and 8 weeks post stent insertion and will be asked about any symptoms related to the stent insertion, and have an assessment of symptomatic GOR using the GerdQ questionnaire ⁸, dysphagia, cough and pain levels at each telephonic follow-up. Telephonic follow-up of these patients will be done by the Clinical Coordinator, who is blinded to which type of stent the patient has received.

All patients will also be referred to the GSH Palliative Care Team. With any symptom reported by a patient or family member that is deemed to possibly require further intervention or treatment, the patient will be requested to return for an evaluation or appropriately managed according to the Palliative Care Distress Algorithm (Appendix 1). All complications will be managed as per standard treatment routinely employed for such a complication at GSH. Any such complications will be documented.

OUTCOME MEASURES

Primary Outcome Measure

The primary outcome will be patient-reported rates of symptomatic volume GOR and objectively measured volume GOR in both study groups. Patient-reported symptomatic volume GOR will be assessed using the validated GerdQ questionnaire (Appendix 2)⁸. This questionnaire has been chosen has it is simple, easy to understand and includes only 6 questions, which are all reflux-related. This questionnaire will be administered to the patient prior to the procedure, to establish a baseline. It will then subsequently be telephonically administered at the scheduled telephonic follow-ups at weeks 1, 2, 4 and 8. The GerdQ questionnaire enables the patient to provide a score at each follow-up interaction which can then be documented and the mean scores between the two groups can then be compared.

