GOR will also be objectively measured on day 1 post stent insertion using scintigraphy. The proposed protocol for scintigraphy is described in Appendix 3. This modality has been chosen as its accuracy compares favourably to pH monitoring⁹, but is much less invasive. It requires the patient to swallow a meal of soft, runny porridge and then undergo imaging. pH monitoring is invasive, requiring the insertion of an uncomfortable nasal probe which stays in-situ for 24 hours, increasing discomfort for the patient but also increasing the hospital stay by a further 24 hours. It is thus deemed inappropriate in this setting.

Secondary Outcome Measures

The secondary outcomes that will be assessed will include immediate technical success rate and any complications related to the stent insertion, subsequent stent-related complications, patient-reported dysphagia score prior to stent insertion, on day 1 post-insertion and then at each of the scheduled telephonic follow-ups and lastly, patient survival at 2 months post stent insertion. Dysphagia assessment will be done using the modified dysphagia scale first published by Mellow and Pinkas and validated for assessing dysphagia after metal stent insertion for oesophageal cancer (Appendix 4)²³. Furthermore, an assessment of the patient's pain level and whether they are coughing will also be documented, using validated pain²⁴ and cough scores²⁵ and pain (Appendix 5 & 6).

Data Collection

The following data parameters will be collected:

- Age
- Gender
- Performance status25 and BMI of the patient at time of stent placement
- Histological type of malignancy (e.g. adenocarcinoma, squamous cell carcinoma or other)
- Reason for inoperability: metastases, locally advanced or poor performance status
- Position of oesophageal malignant stricture (endoscopic measurement in centimetres from the incisors)
- Patient-reported degree of dysphagia prior to stenting
- Patient-reported GerdQ score pre-stenting
- Stent characteristics: anti-reflux vs conventional, length, diameter and brand name of stent
- Immediate technical success rate
- Immediate stent insertion complications:
 - o Bleeding
 - Perforation
 - o Other

- Subsequent stent-related complications during the follow-up period:
 - o Bleeding
 - Perforation
 - Migration
 - Stent occlusion and cause thereof
 - \circ Other
- Quantitative assessment of volume reflux as per scintigraphy (on day 1)
- GerdQ score at follow-up at week 1, 2, 4 and 8

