Using a power calculation for comparison of two continuous data means in a superiority assessment (with GerdQ score means as the primary outcome assessed), assuming a 2-point reduction in GerdQ mean score between the two groups - mean GerdQ score of 9 in the conventional stent control group and a GerdQ score of 7 in the anti-reflux stent group - with a standard deviation of 3, with an alpha level of 5% and power set at 80%, a sample size of 72, with 36 in each arm, is required.

Correlating this to the previous randomised controlled trials, it is noted that these numbers are similar, but slightly higher than previous trials. With concerns that a number of these previous trials were underpowered, a slightly bigger sample size is deemed appropriate.

Time Frame

The study will begin as soon as HREC approval has been granted and the relevant registrations with SANCTR and clinicaltrials.gov have been completed. It is expected to run for 36 months. Interim analyses of the collected data will be performed at 12 and 24 months.

Budget

All research-related costs will be covered by the General Surgery and Surgical Gastroenterology Research Funds.

1. Stents:

Both types of oesophageal stents (conventional and anti-reflux) are currently available at Groote Schuur Hospital and as they form part of the standard treatment of these patients, will not need to be purchased specifically for this research study.

- Scintigraphy: R4000 per investigation x 72 patients = R288 000
- 3. Clinical coordinator:

The clinical coordinator for this trial is already employed by the University of Cape Town and is very active in multiple research projects within the Surgical Gastroenterology Unit. She will thus not need to be renumerated specifically for her assistance in this trial.

4. Other Costs:

This trial will not require specific electronic or other research-related equipment or major stationary costs. All other minor costs will be borne by the study investigators.

TOTAL COSTS:

R288 000

REFERENCES

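### The primary analysis is inconsistent and incompletely specified: two primary outcomes, a sample size for one GerdQ comparison, no deciding week or success rule, and interim analyses with no stated purpose

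*Combined protocol and SAP*

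**What the plan says.** Primary Objective/Hypothesis to be Tested sets out to "compare rates of self-reported, symptomatic volume GOR and objectively measured rates of volume GOR using scintigraphy". Primary Outcome Measure repeats the pairing: "The primary outcome will be patient-reported rates of symptomatic volume GOR and objectively measured volume GOR in both study groups". The two outcomes have equal standing in both places and are described as rates, but no cut-off defines a rate.

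Sample Size takes a different line. It is calculated "with GerdQ score means as the primary outcome assessed", for means of 9 and 7 with SD 3, and concludes that "with an alpha level of 5% and power set at 80%, a sample size of 72, with 36 in each arm, is required".

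On timing, GerdQ has a baseline value, and then "It will then subsequently be telephonically administered at the scheduled telephonic follow-ups at weeks 1, 2, 4 and 8". The planned use of these values is only that "the mean scores between the two groups can then be compared". For scintigraphy, "GOR will also be objectively measured on day 1 post stent insertion using scintigraphy". Appendix 7 lists four scintigraphy results, of which oesophageal reflux is one, with no threshold.

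Statistical Analysis gives one general threshold, p<0.05, and promises inferential statistics for the GOR scores. It names no test and no rule for several comparisons. Under Time Frame, for a trial expected to run 36 months, "Interim analyses of the collected data will be performed at 12 and 24 months".

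**The concern.** Three sections that should identify the same deciding test do not. A reader of the objectives expects two primary results, and a reader of the sample size expects one. Neither can tell which GerdQ week counts, or what happens if GerdQ and scintigraphy disagree. The choice could then be made after the data are seen. A reported p<0.05 would carry an unknown error rate, and the stated 80% power might not apply to the result reported. The background section criticises earlier trials as small and mixed in how they measured reflux, so a trial meant to settle the question needs its deciding test fixed in advance.

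**Working it through.** **1. The plan's own figure.** Inputs from Sample Size: difference 2, SD 3, alpha 5%, power 80%; 1:1 allocation from Interventions. Sidedness is not stated.

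n per arm = 2(z_alpha + z_power)² × SD²/difference²

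- Two-sided 5%: 2 × (1.960 + 0.842)² × 9/4 = 35.3, so 36 per arm and 72 in total. This matches.
- One-sided 5%: 2 × (1.645 + 0.842)² × 9/4 = 27.8, so 28 per arm. This does not match.
- With a t-test the requirement is 36.3 per arm, and power at 36 is 79.7%.

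The 72 is correct for one two-sided GerdQ test. It leaves nothing for a second primary outcome, a choice of week, or testing at interims.

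Steps 2 to 5 use t-tests or the normal approximation at 36 per arm with complete data. The correlations are assumptions, because the documents give none.

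**2. If either outcome may win at the final analysis.** Independent outcomes: 1 − 0.95² = 9.75%. Simulated at correlation 0, 0.3, 0.5 and 0.7: 9.8%, 9.5%, 9.1% and 8.4%. Counting only results that favour the anti-reflux stent, independence gives 1 − 0.975² = 4.9%, falling to 4.2% at correlation 0.7, against a nominal 2.5%.

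**3. If any of the four GerdQ weeks may win.**

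| Between-week correlation | Two-sided | Favouring anti-reflux stent only |
|---|---|---|
| 0.3 | 17.4% | 8.7% |
| 0.5 | 15.5% | 7.9% |
| 0.7 | 13.2% | 6.6% |
| 0.9 | 9.5% | 4.7% |

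If correlation instead decays with the time between weeks (0.95 down to 0.7 per week), the two-sided rate is 10.6-16.6%.

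**4. If both outcomes must win, with GerdQ at one fixed week.** When one outcome is truly null, both can be significant no more often than that one is, so the error at a single final analysis stays within 5%. The cost is power. Assume scintigraphy has the same standardised effect as GerdQ, 2/3 = 0.67. Joint power is 0.797² = 63.5% at correlation 0, and 66.1%, 67.9% and 70.4% at 0.3, 0.5 and 0.7.

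**5. Interims (conditional).** Suppose p<0.05 at any of three equally spaced looks could support a claim. For one outcome the two-sided error is then 10.7%. If the looks allow no early stop and no claim, the final test is unaffected.

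**6. Splitting alpha.** At 0.025 per outcome, GerdQ power at 36 per arm is 70.4% (t-test) or 72.1% (normal). For 80% power, 45 (t-test) or 43 (normal) per arm are needed.

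**7. Power by GerdQ week.** The background section gives median survival of 15 weeks from diagnosis, or 10.7 weeks with complete obstruction. Assume exponential survival counted from stenting and no other loss, so that the fraction alive is 0.5^(week/median).

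| Week | Median 15: alive per arm | t-test power | Median 10.7: alive per arm | t-test power |
|---|---|---|---|---|
| 1 | 36 × 0.955 = 34 | 77% | 36 × 0.937 = 34 | 77% |
| 8 | 36 × 0.691 = 25 | 64% | 36 × 0.596 = 21 | 56% |

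**The case against.** Much of the primary analysis is stated: a superiority hypothesis, a comparison of mean GerdQ scores, day 1 for scintigraphy, p<0.05, and inputs that reproduce 72. Sample Size calls GerdQ the primary outcome, and scintigraphy is introduced as something measured in addition, which suggests that GerdQ leads. This stands, and it is why the plan is incompletely specified rather than undefined. It does not remove the conflict with the two sections that define objectives and outcomes, and it leaves the week open.

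A reader might infer that the trial's false-positive rate is 8-17%. The documents do not support that as a flat statement. The outcomes are joined by a plain *and*, and the outcome section speaks of a single primary outcome, so requiring both is at least as natural a reading. No section says that either outcome, or any week, suffices. Those two-sided rates also include results where the anti-reflux stent looks worse. For a hypothesis of reduced reflux, the relevant figures are 4-5% and 5-9% against 2.5%.

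A reader might also infer that the 12- and 24-month analyses already inflate the error. They do so only if a significant result there could be acted on or claimed. The plan mentions no early stopping or early claim, and it rules out neither. The interim point is therefore a request for a stated purpose.

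The correlations are assumed. Even so, every value in the ranges shown exceeds the nominal level when either outcome or any week may win.

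**Conclusion.** The concern holds as an inconsistency with missing rules, and it should be fixed before any comparative data are examined. The sample size arithmetic is right, but it covers one of the two outcomes called primary. The stated 5% and 80% hold together only if GerdQ at one fixed week is the sole primary outcome, no claim can be made at an interim, and close to 36 per arm are assessed at that week. Other readings give up either the error rate (steps 2 and 3) or the power (step 4). The size of the departure rests on assumed correlations, on an equal scintigraphy effect for the joint power, and on exponential survival for power by week. The textual conflict rests on none of these.

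**What to change.** **Reconcile the objectives, the outcome section and Sample Size.** The simplest option has four parts:

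- Name the between-arm difference in mean GerdQ at one stated week as the single primary outcome, two-sided 0.05.
- Replace the wording about rates with mean score.
- Make the other GerdQ weeks secondary.
- Test day-1 scintigraphy second, on one named reflux measure, at 0.05 and only if GerdQ is significant.

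If two equal primaries are kept and either may win, test each at 0.025 and restate GerdQ power at 36 per arm as about 70%. If both are required, say so and restate the joint power. In both cases the GerdQ week still has to be named.

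**State the purpose of the interims.** Either limit the 12- and 24-month analyses to recruitment, data quality and safety with no between-arm GOR test, or give a group-sequential boundary. As one example, O'Brien-Fleming limits for three equally spaced looks are nominal p of about 0.0005, 0.014 and 0.045, recalculated from the numbers actually assessed. Power would be 80.1% against 80.7% without looks (normal approximation).

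**Cost.** The leading option is mostly wording, but scintigraphy loses equal status and the power depends on the week. Name an early week or restate the power for the week chosen, and state how deaths before it are handled. Under the survival assumption above, keeping 36 assessed per arm would need 38-39 enrolled per arm for week 1 (36/0.955 to 36/0.937) and 53-61 for week 8 (36/0.691 to 36/0.596).

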Appendix 4: Dysphagia Score

Appendix 5: Pain Score – Visual Analog (Face) Score

Appendix 6: Simplified Cough Score

Appendix 7: Proposed Data Sheet

Appendix 1 : Palliative Care Distress Management Algorithm

Appendix 2: GerdQ score⁸

Frequency score (points) for symptom

Question	0 day	1 day	2–3 days	4–7 days	
1. How often did you have a burning feeling behind your breastbone (heartburn)?	0	1	2	3	
2. How often did you have stomach contents (liquid or food) moving upwards to your throat or mouth (regurgitation)?	0	1	2	3	
3. How often did you have a pain in the centre of the upper stomach?	3	2	1	0	
4. How often did you have nausea?	3	2	1	0	
5. How often did you have difficulty getting a good night's sleep because of your heartburn and/or regurgitation?	0	1	2	3	
6. How often did you take additional medication for your heartburn and/or regurgitation, other than what the physician told you to take? (such as Tums, Rolaids, Maalox?)	0	1	2	3	

Appendix 3: Gastro-oesophageal Scintigraphy Protocol

The following standardised protocol is provided by the Groote Schuur Hospital Nuclear Medicine Department for gastric emptying, including GOR assessment:

An Oats meal is given to the patient as part of the study:

- Prepare the Oats meal (soft, runny consistency) before taking the patient to the camera room
- Also prepare a small radioactive marker, using a small piece of cotton-wool, to put on the Xiphisternum.
- Once the radioactive meal has been prepared, take the patient to the camera room, and explain the procedure on how the patient must eat the radioactive meal, especially in line with Radiation Protection.
- Ensure that the patient details are entered on the acquisition station, that a workflow is ready for the first acquisition, and that the patient is ready for scanning.
- Remove the patient's clothing from the waist up and place the radioactive marker on the Xiphisternum of the patient. Give patient a gown to put on.
- Diabetic patients on Insulin (oral-insulin combo pts incl.): check how much Insulin the patient needs to take, the patient needs to take half the dose before eating the meal, irrespective if the patient took half a dose of Insulin earlier to lower the glucose.
- Give the patient an apron and a pair of gloves to put on, before handing the radioactive meal to the patient.
- The patient needs to finish the meal within 10 min.
- Immediately after the patient finished the radioactive meal, wipe the patient's mouth with paper towel or rinse the mouth, get the patient on the bed and immediately start imaging.
- Immediately after the completion of the meal, the patient is positioned in front of the camera. The study can be acquired on standing, sitting or supine.
- The same position should be used throughout the study with the camera heads at the same distance from the patient. Document all the

Radiopharmaceutical:

- **Radioisotope:** Technetium-99m (^{99m}Tc)
- Pharmaceutical: Tin-Colloid (SnColl)
- Physical T_{1/2}: 6.02 hours
- Principle photo-peaks: 140 keV
- **Dose:** 20-30 MBq

Imaging Protocol:

- Collimator: Low Energy High Resolution (LEHR)
- **Starting time post injection:** Immediately after the patient has finished the radioactive Oats meal.
- Note: a new acquisition series needs to be opened for each acquisition!
- Static Acquisition:
 - Series: Name the acquisition series according to the time of imaging post last +swallow! The first image will be named the exact time after last swallow (e.g. STATIC 3min), and the rest of the images will be named according to the imaging protocol! (STATIC 0min [i.e. immediately after last swallow], 1hr, 2hr, 3hr, and 4hr)
 - **Zoom:** 1.0
 - Camera Preset: Tc99m-NMG
 - Detectors: Both Detectors
 - Time per view: 60 sec
 - View Labels: Label each view according to patient-to-detector orientation, as well as the time post last swallow (e.g. **Detector 1:** ANT 5min, **Detector 2:** POST 5min).
 - **Orientation:** Head Out
- After the *STATIC* **4hr** image, show the Nuclear Medicine Physician to see if any further imaging is required.

Sources of Error:

- Vomiting after meal ingestion
- Poor labelling
- A nonstandard meal
- A marked variation in the environment, such as noise, lighting, or temperature during imaging. Emotional fluctuations, such as fear of the medical environment, anxieties about results, anger after a long wait for the study to begin

Suggested Standard Meal For Gastro-oesophageal Scintigraphy

- Jungle Oatso Easy 50g satchet
- Protifar 14g powder
- Sugar or Replace 10g *
- Boiling water 180 ml
- Add boiling water to the dry ingredients
- Stir briskly
- Add and mix 20-30 MBq of Tc99m-Tin colloid
- *NOTE
- Replace is tasteless but provides the same amount of carbohydrate as sugar does. In order to adjust for individual patient sweet taste preference, the total (10g) sugar or Replace should always remain constant, but the proportion of each can be changed. For example:
- 5 g sugar + 5 g Replace
 - OR
- 10 g sugar + 0 g Replace

[figure not shown]
OR

• 0 g sugar + 10 g Replace

Appendix 4: Dysphagia Score²³

- 0 = normal/no dysphagia
- 1 = ability to eat some solid food
- 2 = ability to eat semisolids only
- 3 = ability to swallow liquids only
- 4 = complete dysphagia (inability to swallow saliva)

Appendix 5: Pain Score – Visual Analog (Face) Score²⁴

Appendix 6: Simplified Cough Score²⁵

Score	Daytime Cough Symptoms	Nigh-time Cough Symptoms	
0	No cough	No cough	
1	Transient cough occasionally during the daytime	Transient cough before sleep or occasional cough during the night	
2	Frequent cough mildly affecting daily life	Cough mildly affects night sleep	
3	Frequent cough severely affecting daily life	Cough severely affects night sleep	

